7.1.6 Non-Relapse Mortality (NRM)

Any death that occurs after HCT not attributable to relapse of the underlying disease will be considered a non-relapse death.

7.1.7 Chronic GVHD

The occurrence of chronic GVHD as defined by NIH consensus criteria requiring systemic treatment, including date of diagnosis, will be recorded.

7.1.8 Relapse

Relapse, including date of relapse, of the underlying malignancy will be recorded.

7.2 SAFETY/TOXICITY DEFINITIONS

7.2.1 Itacitinib monotherapy was generally safe and well tolerated in clinical studies of 777 adults including healthy subjects and patients with psoriasis or myelofibrosis (*Itacitinib investigator brochure v9, Feb 9 2017*). There were no non-hematologic adverse events that occurred in >1% of subjects. Hematologic adverse events grade 3 or 4 included decreased hemoglobin (12.4%), decreased platelet count (9.1%) and decreased neutrophil count (1.4%) of patients. These hematologic

adverse events were most common in patients with myelofibrosis and improved with higher doses of itacitinib³⁸ suggesting they were more likely due to the underlying disease than itacitinib. There were no toxicities observed in a study of itacitinib plus steroids in patients with acute GVHD that were felt to be related to itacitinib administration. Known or plausible toxicities that may be related to itacitinib will be reported.

7.2.2 Hematologic Toxicities

Hematologic toxicities will be graded according to CTCAE v4 criteria.

7.2.3 Infectious Toxicities

Infections, including serious and/or life-threatening infections, are common in patients who undergo HCT. MAGIC clinical trial practice requires the reporting of any life-threatening infection as defined by the Blood and Marrow Transplant Clinical Trials Network grade 3 (see Appendix B for further details).

Grade 3 Bacterial Infections:

- a. Bacteremia with deep organ involvement
- b. Severe sepsis with bacteremia
- c. Fasciitis requiring debridement
- d. Pneumonia requiring intubation
- e. Brain abscess or meningitis without bacteremia
- f. Clostridium difficile toxin positive stool with toxic dilatation or renal insufficiency with/without diarrhea.

Grade 3 Fungal Infections:

- a. Fungemia, including candidemia
- b. Proven or probable invasive fungal infections (e.g. Aspergillus, Mucor, Fusarium, Scedosporium)
- c. Disseminated fungal infections (e.g. multifocal pneumonia, presence of urinary/blood antigen, CNS involvement) with Histoplasmosis, Blastomycosis, Coccidiomycosis or Cryptomycosis
- d. Pneumocystis jiroveci pneumonia

Grade 3 Viral Infections:

- a. Severe VZV infection with either associated coagulopathy or organ involvement
- b. CMV end organ involvement (e.g. pneumonitis, enteritis, retinitis)
- c. EBV Post-transplant lymphoproliferative disorder (PTLD)
- d. Adenovirus with end organ involvement (except adenoviral conjunctivitis or upper respiratory tract disease)
- e. All lower respiratory tract viruses
- f. Viral encephalitis or meningitis

Grade 3 parasitic infections:

- a. Toxoplasmosis involving the CNS
- b. Strongyloides hyperinfection

Non-microbiologically documented infections:

- a. Any acute pneumonia requiring mechanical ventilation
- b. Severe sepsis without an identified organism

In addition, the following non-BMT CTN infections will be reported: bacteremia requiring systemic antibiotics and CMV and EBV reactivation requiring treatment.

7.2.4 Bacteremia

The date, identification, and treatment of bacteremia requiring systemic antibiotic therapy will be reported.

7.2.5 Viral Reactivations

Because viral reactivations often require treatment in the HCT population, even in the absence of end organ disease, the following viral infections/reactivations and their treatment, if any, will be reported:

The date, anatomical site or body fluid (e.g., blood, nasopharyngeal swab, stool, etc.), and method of detection for CMV, EBV, HHV6, VZV, HSV and adenovirus will be reported.

7.3 Safety/Tolerability

Analyses will be performed for all patients having received at least one dose of study drug. The study will use the CTCAE version 4.0 for reporting of adverse events (http://ctep.cancer.gov/reporting/ctc.html).

7.4 Children as a Special Population

This study will enroll minor subjects age 12-17 years. It is important to include children in this clinical trial for GVHD because children are not only susceptible to the same risks from standard care with systemic steroids as adults but are particularly at risk for permanent skeletal damage^{20,21}. Although itacitinib has not been studied in children, the JAK inhibitor ruxolitinib has been used therapeutically in children as a treatment for GVHD³⁴ and as monotherapy in a phase I trial of 49 children with refractory cancer⁴³. The side effect profile was the same as in adults with no unexpected toxicities. Ruxolitinib is considered safe for use in children based on the phase I trial and experience with this agent in children continues to grow^{44,45}. Itacitinib has not yet been tested in children but we do not expect children to experience different toxicities than adults. In the interest of subject safety we will closely monitor the efficacy and toxicity of itacitinib in patients under the age of 18 years and, in the event of any unexpected toxicities or lack of efficacy, accrual to children will be halted (see section 12.0).

8.0 ADVERSE EVENTS

8.1 Itacitinib

For the most recent safety update, please refer to the current Investigator's Brochure or Study Agent Prescribing Information.

8.1.1 Contraindications

Patients who have had an allergic reaction to itacitinib or any other JAK inhibitor.

8.1.2 Special Warnings and Precautions for Use: none

8.2 Adverse Event Reporting Requirements

Adverse event (AE) monitoring and reporting is a routine part of every clinical trial and is done to ensure the safety of subjects enrolled in the studies as well as those who will enroll in future studies using similar agents. Data on adverse events will be collected from the time of the initial study treatment (day 0) through 30 days after the last dose of itacitinib. Any serious adverse event that occurs more than 30 days after the last dose of itacitinib that is considered related to the study treatment must also be reported. Serious Adverse Events (SAEs) will continue to be followed until:

- Resolution or the symptoms or signs that constitute the serious adverse event return to baseline;
- There is satisfactory explanation other than the study treatment for the changes observed; or
- Death.

The investigator is responsible for the detection, documentation, grading and assignment of attribution of events meeting the criteria and definition of an AE or SAE. The definitions of AEs and SAEs are given below. It is the responsibility of the principal investigator to ensure that all staff involved in the trial is familiar with the content of this section.

Any medical condition or laboratory abnormality with an onset date before initial study treatment administration is considered to be pre-existing in nature. Any known pre-existing conditions that are ongoing at time of study entry should be considered medical history.

All events meeting the criteria and definition of an AE (CTCAE grade 3 or higher) or SAE, as defined in Section 8.3, occurring from the initial study treatment administration through 30 days following the last dose of the study treatment or study intervention must be recorded as an adverse event in the patient's source documents and on the CRF.

8.3 Definitions

8.3.1 Adverse Event

An adverse event (AE) is any untoward medical occurrence in a patient receiving study treatment and which does not necessarily have a causal relationship with this treatment. An AE can be any unfavorable and unintended sign (including an abnormal laboratory finding), symptom, or disease temporally associated with the use of an experimental intervention, whether or not related to the intervention.

- Diagnostic and therapeutic non-invasive and invasive (i.e., surgical) procedures will not be reported as adverse events. However, the medical condition for which the procedure was performed must be reported if it meets the definition of an adverse event unless it is a pre-existing (prior to protocol treatment) condition.
- Event reporting for GVHD treatment protocols can be complicated and confusing for investigators, data managers, and regulatory oversight bodies because patients typically develop numerous complications as part of the typical treatment course not related to study therapy. Furthermore, transplant-related complications often occur both simultaneously and in series, as one complication leads to a series of downstream events. Therefore, a well-conceived event reporting plan separates background transplant and GVHD noise as might be seen with any transplant where GVHD develops from study related events that are relevant to patient safety. On this study, we will not report any CTCAE grade 1 and 2 adverse events (which make up the majority of events) unless the investigator determines the event should be reported to protect subject safety.
- It is common for HCT recipients to experience multiple complications as part
 of the transplant itself that are unrelated to exposure to investigational agents.
 Symptoms of the original or targeted disease are not to be considered adverse
 events for this study except for hematological toxicities as defined below. From
 start of study treatment through 30 days from last dose of itacitinib, symptoms
 related to the conditioning regimen or GVHD will not be reported unless the
 event is both serious (see section 8.3.2) and considered by the investigator to

also be possibly, probably, or definitely related to itacitinib. After 30 days from the last dose of itacitinib, adverse events should only be reported if they are both serious and probably or definitely related to itacitinib. Events that are unlikely or unrelated to itacitinib are not required to be reported. Reporting of such events should include the investigator's assessment as to whether the event should be attributed to any of the HCT procedure itself, GVHD, exposure to immunosuppressive agents other than itacitinib, and itacitinib. An event may be attributable to all, some, or one of these categories.

• Abnormal laboratory values or test results constitute adverse events only if they induce clinical signs or symptoms or require therapy and otherwise meet the criteria for a reportable adverse event as defined above. They are to be captured under the signs, symptoms or diagnoses associated with them.

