2.3 Primary Endpoint

Proportion of patients who achieve CR or PR by day 28 of treatment with itacitinib without the addition of any other systemic GVHD treatment including steroids.

CR is defined as absence of GVHD symptoms. PR is defined as improvement in one or more organs involved with GVHD symptoms without progression in other organs. For a response to be scored as CR or PR on day 28, the patient must be in CR or PR on day 28 and have had no intervening systemic therapy for acute GVHD other than itacitinib.

Secondary endpoints:

- Cumulative incidence of steroid-refractory GVHD (defined as GVHD that worsens (increase by one or more grade) after 3 days, or fails to respond to treatment within 7 days (for GVHD grade III) or 14 days (for GVHD grade II) or 2nd line therapy beyond systemic steroid treatment is begun within 28 days of starting steroids.
- 2. Distribution of maximal GVHD grade (I-IV) by day 28 after starting treatment with itacitinib
- 3. Cumulative incidence of serious infections (defined as bacteremia, CMV infection needing treatment, EBV infection needing treatment, or invasive fungal infection)
- 4. Overall survival at 6 and 12 months
- 5. Cumulative incidence of NRM at 6 and 12 months
- 6. Relapse rate at 6 and 12 months
- 7. Cumulative incidence of chronic GVHD requiring systemic steroid treatment by one year from enrollment

8. Cumulative steroid dose (over 4 weeks) in patients who receive steroids as second line therapy

Safety endpoints

1. Number and proportion of patients developing reportable AEs and SAEs according to relatedness to study drug and stratified by severity

Exploratory endpoints

1. GVHD biomarker concentrations (ST2 and REG3) and their associations with clinical endpoints at day 28 after starting treatment with itacitinib

The two hypotheses are: 1) that GVHD biomarkers will remain low in study patients who respond to itacitinib treatment, but will rise in non-responders and (2) biomarker concentrations will be equivalent to those in historical control patients who respond to steroid treatment for low risk GVHD.

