8.5 Serious Adverse Event Reporting Guidelines

The Sponsor Investigator will report SAEs to regulatory bodies and to the participating sites in the following manner:

Sponsor SAE Reporting

Event occurring	Repo	ort to:	Event occurring	Report to:		
30 Days post last itacitinib dose	FDA / IRB/Incyte	Consortium	post last itacitinib dose	FDA / IRB/ Incyte	Consortium	
All SAEs; ✓ Expected or Unexpected ✓ Possible, Probable, or Definite	24 hours from knowledge	Monthly	 SAEs – ✓ Expected ✓ Probable or Definite OR ✓ Unexpected ✓ Possible, Probable or Definite 	24 hours from knowledge	Monthly	

- 8.5.2 The Principal Investigator must be notified within 3 business day of study team's knowledge of any event meeting the criteria and definition of a serious adverse event, regardless of attribution, occurring during the study or within 30 days of the last administration of the itacitinib. Incyte should be notified by the PI within 24 hours to enable reporting to regulatory authorities as required.
- 8.5.3 The investigator must report all events meeting the criteria and definition of a serious adverse event that are unexpected and possibly related (definite, probable or possible to study treatment administration) to the local IRB as per local IRB policy.
- 8.5.4 All Serious Adverse Events will be reported using the Serious Adverse Event form within 3 days of first awareness of the event to the MAGIC Data Coordinating Center. A copy of the form should be sent to the MAGIC Coordinator via email to **[contact]**.

The MAGIC Data Coordinating Center will disseminate information regarding serious adverse events to the participating sites within 3 days of review of the information by [name] if the event(s) is believed to be related (i.e. probably or definitely) to the study medication. All other Serious Adverse Events will be discussed on monthly webinars held with all participating centers (see section 12).

The Principal Investigator will be responsible for reporting of events to the FDA and supporters, as appropriate and defined in the regulations under 21 CFR 312.32.

8.5.5 SAE/Pregnancy Reporting to Incyte:

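### For serious adverse events more than 30 days after the last dose, section 8.3.1 leaves out those judged possibly related, while section 8.5 requires the unexpected ones to be reported

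*Combined protocol and SAP*

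**What the plan says.** All references are to the combined protocol and SAP.

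- **8.2** collects adverse events through 30 days after the last dose. Grade 3 or higher events and SAEs, as defined in 8.3, go on the CRF. A later SAE "that is considered related to the study treatment must also be reported"; the level of relatedness is not stated.
- **8.3.1**, after 30 days: "adverse events should only be reported if they are both serious and probably or definitely related to itacitinib". The next sentence reads "Events that are unlikely or unrelated to itacitinib are not required to be reported" and gives no period of its own. Through 30 days, symptoms of conditioning or GVHD are reported only if serious and at least possibly related.
- **8.5 table** (sponsor reporting). The first column, for the period to 30 days, covers all SAEs judged "Possible, Probable, or Definite". The second column covers expected SAEs judged probable or definite, and unexpected SAEs judged possible, probable or definite. Both go out within 24 hours.
- **8.5.2** has the principal investigator notified of any SAE "regardless of attribution, occurring during the study or within 30 days of the last administration of the itacitinib".
- **8.5.3** has the investigator report unexpected SAEs that are related ("definite, probable or possible to study treatment administration) to the local IRB as per local IRB policy"), with no time limit.
- **8.5.4** sends all SAEs to the coordinating center within 3 days, with no filter on relatedness and no time limit.
- **2.3** gives the safety endpoint: "Number and proportion of patients developing reportable AEs and SAEs according to relatedness to study drug and stratified by severity".

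**The concern.** The sections use different relatedness thresholds for the same late event. In 8.4.2, Possible is a level of its own on a five-point scale, so it matters whether a rule starts at Possible or at Probable. The level at issue, unexpected and possibly related, is where an unrecognized drug effect would first show. The trial has no control arm, and most complications in these patients have a ready explanation in GVHD or the transplant, so a cautious investigator may often choose Possible. Section 7.4 also says that itacitinib has not been tested in children and that accrual of children will halt on unexpected toxicities. That commitment depends on unexpected events reaching the people who decide.

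A second, smaller matter is the safety endpoint. It counts reportable events, and the plan does not give that word one meaning.

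**Working it through.** No sample size, power or error rate is involved. The check sets the rules side by side and then measures the period they govern.

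**Step 1. An SAE more than 30 days after the last dose**

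| Section | Unexpected, possible | Expected, possible | Probable or definite | Unlikely or unrelated |
|---|---|---|---|---|
| 8.2 | not determined | not determined | report | no duty stated |
| 8.3.1 | do not report | do not report | report | not required |
| 8.5 table, second column | report | not listed | report | not listed |
| 8.5.2 | notify, if follow-up counts as during the study | same | same | same |
| 8.5.3 | report to local IRB | not covered | report if unexpected | not covered |
| 8.5.4 | report to coordinating center | report | report | report |

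The first column is a direct contradiction: 8.3.1 says no, while 8.5.3, 8.5.4 and the 8.5 table say yes. For expected events judged possible, 8.3.1 and the table agree and only the blanket rule in 8.5.4 differs (8.5.2 also, if it reaches follow-up). For probable or definite events the reporting thresholds do not conflict.

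**Step 2. How far this rests on the table.** The heading of the second column is damaged in the text available, so reading it as the period after 30 days is an inference from the first column. Sections 8.5.3 and 8.5.4 show the conflict without it.

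**Step 3. Whether 8.2 settles it.** It does not. Section 8.5.3 counts possible as related. Section 8.5.4, on passing events to sites, glosses related as probably or definitely. Section 8.2 fits either use, so it neither proves the conflict nor resolves it.

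**Step 4. Events through 30 days.** For SAEs judged possible or higher, 8.2, 8.3.1 and the first column of the table agree. For events judged unlikely or unrelated, 8.2 (CRF), 8.5.2 and 8.5.4 apply no relatedness filter, though 8.5.2 and 8.5.4 cover SAEs only. Section 8.3.1 excludes conditioning and GVHD symptoms unless they are serious and at least possibly related. Because 8.2 points to the definitions in 8.3, one site may read that exclusion into the CRF rule and another may not. This is an unclear boundary, not a flat contradiction.

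**Step 5. Length of the late period.** Inputs: 56 days of treatment and a ten-week cap (5.5), day 86 as 30 days after completion (6.2), maintenance for responders only (6.2 table notes), final assessment at day 365 (6.2 table).

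- 56-day completer: 56 + 30 = day 86; 365 − 86 = 279 days; 279/365 = 76%.
- Treatment to the ten-week cap: 70 + 30 = day 100; 365 − 100 = 265 days; 265/365 = 73%.
- Induction only, no missed doses: 28 + 30 = day 58; 365 − 58 = 307 days; 307/365 = 84%.

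For patients who stop earlier to start steroids, the late period is longer still.

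**The case against.** The strongest reply is that 8.3.1 is not a site's only instruction. Section 8.5.4 tells sites to send all SAEs, 8.5.3 covers the event in question, and 8.5.2 may do so. A site that follows 8.5 would report it. That is true, but such a site would breach the word only in 8.3.1. Nor does it help to say that the table binds the sponsor and 8.3.1 binds the sites, since the sponsor cannot forward what was never sent.

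It can also be said that a higher late threshold is deliberate. Section 8.3.1 explains the wish to separate transplant and GVHD background from study-related events, and the table itself starts at probable for late expected SAEs. This stands as a reason for some late filter. It does not explain why the filter differs between sections for unexpected events.

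Important late outcomes are collected whatever their attribution: defined infections to day 90, survival, relapse and chronic GVHD at days 180 and 365, and six-month non-relapse mortality under a stopping rule. This also stands and limits the loss to other late toxicities.

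A reader might infer two stronger things.

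- *That the safety endpoint cannot be tabulated.* The documents do not support this. The endpoint counts only reportable events, and 8.2 captures grade 3 or higher events and SAEs through 30 days without a stated relatedness filter. The sentence on unlikely or unrelated events directly follows the late rule and most naturally covers late events only.
- *That the loss can be sized from the itacitinib-plus-steroid study in 9.1*, where 22 of 29 subjects had an SAE and 7 had a treatment-related one: (22 − 7)/29 × 70 = 36 patients. These are not late-window figures. They come from patients with moderate to severe GVHD on high-dose steroids, and such events through 30 days would fall under 8.2, 8.5.2 and 8.5.4.

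**Conclusion.** The plan is wrong as written on one rule. For a late, unexpected SAE judged possible, 8.3.1 directs sites not to report what 8.5.3 and 8.5.4 require and, on the inferred reading of its second column, what the 8.5 table requires too. As a result such events can go unsent, and the reportable set behind the safety endpoint may differ among the 13 listed centers.

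The number of affected events cannot be derived from the documents. The rule governs about three quarters of a treatment completer's year (73% to 76%), and more for those who stop early. The ambiguity through 30 days is secondary and needs clarifying in the same edit.

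**What to change.** 1. Change the late rule in 8.3.1 to match 8.5: after 30 days, report unexpected SAEs judged possible, probable or definite, and expected SAEs judged probable or definite.
2. Define related in 8.2 in the same terms.
3. Reconcile the blanket rule in 8.5.4 with this, by stating either its period or that the coordinating center receives every SAE throughout follow-up. Say in 8.5.2 whether follow-up counts as during the study.
4. State that the 8.3.1 sentence on unlikely or unrelated events applies only after 30 days.
5. Reconcile the 8.3.1 exclusion of conditioning and GVHD symptoms through 30 days with the CRF rule in 8.2 and the notification rule in 8.5.2.
6. Define reportable in 2.3 and 11.1 by reference to the resulting rule.

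The cost is wording in these sections and a few more late SAE reports. The design and sample size do not change.

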8.3.2 Serious Adverse Event

An adverse event is considered "serious" if, in the view of the investigator, it results in any of the following outcomes:

o Death

If death results from (progression of) the disease, the disease should be reported as event (SAE) itself.

- A life-threatening adverse event An adverse event is considered 'life-threatening' if, in the view of either the investigator, its occurrence places the patient or subject at immediate risk of death. It does not include an adverse event that, had it occurred in a more severe form, might have caused death.
- o Inpatient hospitalization or prolongation of existing hospitalization for ≥24 hours.
- A persistent or significant incapacity or substantial disruption of the ability to conduct normal life functions
- A congenital anomaly/birth defect

• Important medical event

Any event that may not result in death, be life-threatening, or require hospitalization may be considered serious when, based upon appropriate medical judgment, they may jeopardize the patient and may require medical or surgical intervention to prevent one of the outcomes listed in this definition of "Serious Adverse Event". Examples of such medical events include allergic bronchospasm requiring intensive treatment in an emergency room or at home; convulsions that do not result in inpatient hospitalization or the development of drug dependency or drug abuse.

As additional guidance, previously planned (prior to signing the informed consent form) surgeries should not be reported as SAEs unless the underlying medical condition has worsened during the course of the study and the definitions in section 8.3.1 are met. Preplanned hospitalizations or procedures for preexisting conditions that are already recorded in the patient's medical history at the time of study enrollment should also not be considered SAEs. Hospitalization or prolongation of hospitalization without a precipitating clinical AE (for example, for the administration of study therapy or other protocol-required procedure) should not be considered SAEs. However, if the preexisting condition worsened during the course of the study, and the reporting requirements in section 8.3.1 are also met, it should be reported as an SAE.

